Participants: We will recruit approximately 80 individuals who have PD and documented cognitive impairment and 80 caregivers from ongoing studies of neuropsychological functioning in PD (PI: [name]). Over-recruitment by 10% will also be instituted to account for subject attrition or unusable data and to ensure a final sample size of 20 participants (10 x 2 CogSMART groups) for Aims 1 and 2 and 60 for the Exploratory Aim. All participants will be screened and excluded if they have a history of significant head trauma, other neurologic or major psychiatric disorders, history of developmental learning disorder, substance dependence, or any contraindication to participating in the cognitive treatment. The participants' diagnosis of Parkinson's disease will be confirmed by participating neurologists and cognitive impairment (i.e., MCI or dementia) will be confirmed via neuropsychological testing and the consensus of the neuropsychologist investigators (Drs. [name] and [name]). We will also recruit any identified and consistent caregivers of the participants to complete several questionnaires regarding the participant's quality of life and daily functioning prior to and following (immediately, 3- and 9-months) the intervention. All caregivers will be asked to participate if they do not have any known memory impairment, dementia, or another condition which would prevent them from accurately completing the questionnaires.

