Procedures: PD participants: Appropriate individuals will be provided information about the study and study staff will contact those who agree. After receiving detailed information about the study, those who wish to participate will provide informed consent prior to participating in the study. Although participants will be screened for inclusion/exclusion criteria prior to study entry, if, during the course of any of the following assessments exclusionary information becomes available, that participant's data will not be analyzed for the present study. Those passing basic screening procedures will come to the VA to consent to the study. If they consent to participate, PD participants will undergo neuropsychological baseline testing in the same visit. Research assistants trained in neuropsychological testing will administered the neuropsychological assessments to the subjects. Their VA chart, if applicable, will not be reviewed until after the participant has consented to participate. Further, all PD participants will be able to continue with any standard clinical care that they have been participating in or may be recommended by their doctor during the course of their participation in the study. After testing, PD participants will be randomized to either the treatment group or a wait-list control group upon consent and prior to any assessment or treatment by a research assitant. Individuals will be randomized into the treatment vs. waitlist groups by alternating the assignments serially per each qualifying subjects' ID number that is assigned upon study entry. In other words, subjects #'s 1100, 1102, 1104, etc will be assigned to the treatment group and subjects 1101, 1103, 1105, etc will be assigned to the waitlist group. Those randomized to receive treatment will attend a group cognitive rehabilitation psychoeducation program, which will meet once per week for 10 weeks. Groups will consist of 8-10 individuals and will be lead by a postdoctoral fellow and/or an appropriately trained individual who is blinded to the participants' neuropsychological test results.

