Approximately 240 subjects in total will be recruited for this study: 20 PD patients to participate in CogSMART only (no imaging), up to 100 PD patients to participate in CogSMART and the imaging protocol, and 120 caregivers. The PD patients will range in age from 55-95. No patients under 55 will be imaged.

One hundred twenty individuals who have PD and documented cognitive impairment will be recruited from ongoing studies of neuropsychological functioning in PD (PI [name]). Over-recruitment by 10% will also be instituted to account for subject attrition or unusable data and to ensure a final sample size of 20 participants (10 per treatment and 10 per wait list group) for Aims 1 and 2 and up to 100 participants for the Exploratory Aim. All PD participants will be screened and excluded if they have a history of significant head trauma, other neurologic or major psychiatric disorders, history of developmental learning disorder, substance dependence, or any contraindication to participating in the cognitive treatment. PD patients must be medically/clinically stable in order to be included in this study. The participant's Parkinson's disease diagnosis will be confirmed by the participating neurologists, and cognitive impairment (i.e., MCI or dementia) will be confirmed via neuropsychological testing and the consensus of the neuropsychologist investigators (Drs. [name] and [name]). We will also recruit any identified and consistent caregivers (e.g., spouse, friend, relative) of the participants to complete several questionnaires regarding the participant's quality of life and daily functioning prior to and following (immediately, 3- and 9-months) the intervention. All caregivers will be asked to participate if they do not have any known memory impairment, dementia, or another condition which would prevent them from accurately completing the questionnaires.

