The primary safety issues for this study are those related to mental fatigue, boredom and/or anxiety during the intervention or assessment. To ensure the safety and comfort of all subjects, rest breaks are built into CogSMART as well as the neuropsychological assessments. Participants will also be free to discontinue the intervention or testing at any time for any reason or to ask for additional rest breaks or other accommodations to increase tolerability of CogSMART or the paper-and-pencil testing. Home visits will be offered to the participants to increase functional gains, but further inclusion in the CogSMART program 10-week treatment group will not be denied if the participants and/or the caregivers decline this assessment. In general, the study poses no significant increase in risk than what would normally be present in proper clinical management of PD patients. The intervention is offered in a group format and there may be a somewhat greater risk of social discomfort and confidentiality breach than might be present in a non-group format. All group participants, however, will be strictly instructed on the need for confidentiality related to group membership and group proceedings. A tertiary risk might include unintentional disclosure of confidential test information but confidentiality will be strictly maintained in data storage, manipulation, and presentation. Participant identity will be coded immediately upon entry into the study, and neither the participants' names nor any identifying information will be present in the data set. Presentation of the results will involve group data and the subjects' identity will not be disclosed. Given the age and medical condition (i.e., Parkinson's disease) of the participants, it is possible that individuals may experience medical or psychological changes, unrelated to the study that would necessitate early termination of the study. If the individual situation warrants, participants may be able to rejoin a later group. Because this is a psychoeducation group, not a therapy group, there is no expectation that individuals will divulge mental health related information during the 10-week course. However, should any such information arise that causes study staff to be concerned about that participant'

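### Phase I removes a participant's data from analysis when exclusionary information appears at any assessment, without limiting this to ineligibility that existed before allocation

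*Combined protocol and SAP*

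**What the plan says.** Section 9 (Design and Methods, Phase I, Procedures) first notes that screening takes place before study entry. It then provides that if "during the course of any of the following assessments exclusionary information becomes available, that participant's data will not be analyzed" for this study. The assessments that follow are baseline and about 3, 6 and 12 months, in both arms.

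The Phase I exclusions in Section 9 (Participants) are "history of significant head trauma, other neurologic or major psychiatric disorders, history of developmental learning disorder, substance dependence, or any contraindication" to the cognitive treatment. Section 10 (Human Subjects, Phase I) adds that "PD patients must be medically/clinically stable in order to be included in this study". Dementia does not exclude: "cognitive impairment (i.e., MCI or dementia) will be confirmed via neuropsychological testing".

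Allocation is by "alternating the assignments serially per each qualifying subjects' ID number that is assigned upon study entry"; even numbers go to treatment and odd numbers to the wait-list. Its timing is given as "After testing, PD participants will be randomized to either the treatment group or a wait-list control group upon consent and prior to any assessment".

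Section 14 (Potential Risks, Phase I) foresees medical or psychological changes, unrelated to the study, that end participation early, and adds: "If the individual situation warrants, participants may be able to rejoin a later group".

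The Phase I analysis consists of reliable change indexes, change-score comparisons and repeated-measures ANCOVA. No analysis set is defined.

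**The concern.** Removing participants after allocation is usually defensible only if the reason existed before allocation and was judged without knowledge of arm or results. The Phase I sentence requires neither. It removes all of the participant's data, including valid visits completed before the information came to light. Staff who can see an ID know the arm, and a group-blinded examiner is stated for Phase I only in the imaging component.

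Two estimates are exposed. The between-arm comparison (Hypothesis 1a) loses the protection of allocation if exclusions differ by arm. The maintenance hypotheses (1b and 1c) are worded as change within the CogSMART arm, and the wait-list may receive CogSMART between months 3 and 6, so equal exclusion in both arms would not cancel there.

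The statement in Section 9 (Phase II, Participants) that Phase I had no attrition does not settle this, because it does not say how many participants, if any, were removed under this rule.

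**Working it through.** **1. The text.**

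- *When can the rule operate?* At any of four assessments. Three clearly follow allocation. Baseline may as well, because randomization is placed both after testing and before any assessment.
- *Which criteria can change after entry?* Most are worded as history or diagnosis. The open contraindication clause and the stability requirement describe a current state and can change.
- *Which outcomes could be linked?* Cognitive decline is not a trigger, since dementia qualifies. No mood-scale score is an exclusion criterion. Any link to cognition, function or quality of life would be indirect.
- *Who decides?* Not stated, and no masking is required.

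**2. The plan's own figures.** Phase I gives no alpha, power, SD or numeric effect, and no expected number of exclusions, so there is no power figure to reproduce. Section 9 targets final samples of 20 and 60 (20 + 60 = 80), with 10% over-recruitment for attrition or unusable data. It does not say whether the recruitment figure of about 80 includes that 10%. For Aims 1 and 2, 10% of 10 per arm is one participant. Assuming a two-sided 5% test (normal approximation), going from 10 to 9 per arm lowers power from 0.20 to 0.18 at d = 0.5, and from 0.43 to 0.40 at d = 0.8. Lost precision is therefore the minor issue.

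**3. Illustration of bias. All inputs are assumed.** Let the trigger be m ~ N(0,1), with higher values worse. A participant is excluded if m > c, where c = Φ⁻¹(1 − p). Cognition correlates −ρ with m, with ρ = 0.3 or 0.5.

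The mean of m among those kept falls by φ(c)/(1 − p), and mean cognition rises by ρ times that amount:

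| p | φ(c)/(1 − p) | ρ = 0.3 | ρ = 0.5 |
|---|---|---|---|
| 5% | 0.1031/0.95 = 0.109 | 0.033 | 0.054 |
| 10% | 0.1755/0.90 = 0.195 | 0.059 | 0.098 |
| 20% | 0.2800/0.80 = 0.350 | 0.105 | 0.175 |

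- *Within one arm (1b, 1c), or exclusion in one arm only with no true effect:* the shifts are those in the table. If the analysed variable is itself the trigger and p = 10%, simulated type I error for one-arm exclusion is 0.064 at 10 per arm and 0.113 at 30 per arm, against 0.047 and 0.049 with no exclusion.
- *Same rule in both arms, treatment not affecting the trigger:* the shifts cancel (0.195 − 0.195 = 0). Type I error is 0.0485 at 10 per arm and 0.053 at 30.
- *Same rule, treatment lowers m by 0.5 SD, p = 10%:* control loses 10.0% and the treated arm 1 − Φ(1.282 + 0.5) = 3.7%. The treated shift is 0.0816/0.9626 = 0.085. The difference in m becomes 0.50 + 0.085 − 0.195 = 0.390. A true cognitive difference of 0.50 becomes 0.50 + ρ(0.085 − 0.195), which is 0.467 (ρ = 0.3) or 0.445 (ρ = 0.5). Over p of 5% to 20% and effects of 0.3 to 0.5 SD on m, the simulated cognitive shift is −0.01 to −0.08 SD, against treatment.

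**The case against.** The strongest defence is that the sentence deals only with late discovery of ineligibility that screening missed. It follows directly on a clause about screening, most criteria describe history, and the VA chart is not opened until after consent, which makes late discovery likely. On that reading the practice is common and largely harmless. The reading is natural and may be what was meant. It does not remove the point, because the sentence does not say so, two conditions can change after entry, and no masking is required.

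Three stronger readings are tempting, and the documents do not support them:

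- *That the analysed set is selected on outcome.* Nothing states that a new event or a mood-scale score triggers removal. The efficacy indices named for Phase I are cognition, function and quality of life. Decline on the cognitive measures is not exclusionary.
- *That Section 14 contradicts the rule.* Section 14 concerns stopping and rejoining and is silent on data. It leaves a gap about which data are analysed, not a conflict.
- *That the loss of one or two of 10 participants shifts an arm by 0.17 SD (1.539/9) or 0.32 SD ((1.539 + 1.001)/8).* The arithmetic is right, but it assumes that those removed are exactly the worst scorers on the analysed outcome and come from one arm. It is a worst case, not an expected effect.

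It can also be said that Phase I appears to be finished, since Section 9 speaks of its attrition in the past tense. If so, rewriting the procedure changes little, but the count by arm and the sensitivity analysis remain useful.

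**Conclusion.** The point holds as a defect of the written rule: it permits post-allocation selection that may be related to outcome, with no limit to pre-existing facts, no masked decision and no Phase I analysis set to fall back on. Whether any bias occurred is unknown.

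The size cannot be derived from the documents. With the assumed inputs above, between-arm bias is zero when the rule is applied alike and treatment does not affect the trigger. It is up to about 0.08 SD in cognition against treatment when treatment improves the trigger, and 0.033 to 0.175 SD when exclusion occurs in one arm only, with the direction set by which arm loses participants. The same one-arm shifts would apply to within-arm maintenance estimates, in the favourable direction if those removed tend to do worse. These rest on a normal trigger, 5% to 20% exclusion and correlations of 0.3 to 0.5, none of which the plan supplies. The change is worth making; the point does not by itself invalidate Phase I.

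**What to change.** 1. Restrict the rule in Section 9 (Phase I, Procedures) to ineligibility shown to have existed before allocation. Have it judged from records with arm, ID number and outcome scores masked; the ID must be hidden because its parity gives the arm.
2. Analyse all other participants as allocated, with all observed visits, including those who stop or rejoin a later group under Section 14.
3. Report the number and reasons of exclusions by arm, and run one sensitivity analysis retaining everyone. This applies even if Phase I data are already collected.
4. Reconcile the two statements on when randomization takes place, since the meaning of before allocation depends on it.

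The cost is a short protocol clarification, a masked review of any affected records and one additional analysis. The small downside is that a few participants with confounding events stay in and add noise.

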Our projected sample size is consistent with the sample reported on in the preliminary data section ([name] et al., 2008). As we propose to use a similar sample size and the same cognitive rehabilitation program, we anticipate achieving similar medium to large effect sizes in the proposed study. To determine whether CogSMART will improve cognition in PD, we will employ statistical analyses including reliable change indexes to take into account change in neuropsychological test scores over the course of the intervention while also accounting for predicted practice effects. We will compare the treatment and control groups on baseline and three-month change scores. Group comparisons of differences and

changes in neuropsychological test scores between as well as within groups will also be determined via repeated measures (RM) ANCOVAs. Cognitive, functional, and quality of life indices of both participants and caregivers will be of interest in determining efficacy of treatment.

As an exploratory aim, we will recruit 60 additional individuals to complete the protocol as described above and in addition, participate in two (pre/post) hour-long brain imaging (fMRI) sessions. The imaging sessions will consist of a structural brain scanning and participation in an fMRI cognitive task (please see below). Following the baseline evaluation, half of the participants will be randomly assigned to the intervention group ($n = 30$) and participate in the CogSMART program. The groups will be broken up to consist of 8-10 individuals. The remaining participants ($n = 30$) will be assigned to the non-intervention /waitlist ("care-as-usual") group. This group will also be broken down into groups of 8-10 when enrolled in the intervention. Participants will be retested by a group assignment-blinded examiner on the clinical and cognitive battery and imaging protocol following the intervention or waitlist.

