Participants may experience vertigo, tinnitus, optic phosphemes or fasciculations during movement in the 3T magnetic field. These symptoms are generally mild and transient, as will be explained to participants. Testing will be stopped at any time upon request. A physiological reaction (nerve or muscle stimulation) can occur in some individuals during certain imaging sequences if their position in the scanner forms a circuit (e.g., connected hands). Therefore, participants will be asked not to cross arms or legs and will be visually monitored to confirm this. Dizziness, excessive warmth, visual flashes, dots, scintillations, or tactile sensations due to rapidly switching gradients may also occur. Some patients undergoing this procedure become anxious or claustrophobic. If this happens, the subject can stop the procedure at any time. Subjects may experience some discomfort and fatigue from lying still in a confined space during imaging (total acquisition time for a particular MR imaging session will not exceed one hour for any study participant). Secondary risks include the possibility of an abnormal finding on the MRI exam, however, this MRI scan is not being done for clinical purposes, and is not sufficient for a clinical diagnosis of any brain disorder. We will notify participants and their physician in the event of any abnormal finding. As this is an experimental procedure, there are no alternative treatments, but subjects are free to discontinue participation at any time for any reason.

Sensitive information is not collected at the Keck Center. Patients are only identified by their subject ID number assigned prior to scanning. The VA Consent form is carried to the Keck Center so that the subject can undergo MRI scanning. The VA Consent form is carried back to the VA inside a locked briefcase and stored inside a locked cabinet inside a locked room 1-2304. The consent is not given or any information recorded at the Keck Center, it is mainly utilized to confirm subjects concurrence to undergo the scanning procedure. Then, the subject is assigned a code to identify the scanned images.

Wii participation

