Test anxiety and fatigue will be minimized by explaining the testing procedures, by supportive assurance, and by taking brief rest periods throughout the evaluation. Pre-treatment evaluations will last approximately 2-3 hours and the home visit (optional) will last approximately 30 minutes for the PD participants. The caregivers' participation will last approximately 30 minutes to 1 hour for completion of the interview and questionnaires and if agreed to, they will be involved in the 30-minute home evaluation. Each participant will be offered a home evaluation as part of the evaluation; however, should the participant or their caregiver decline this evaluation, the individual with PD will still be permitted to participate in the 10 week CogSMART treatment group. Each CogSMART session will last approximately two hours. Evaluations will be performed by examiners experienced in working with geriatric and neurologic populations.

In order to protect individuals from a breach of confidentiality, sensitive information will be kept confidential by using coded numbers instead of names to identify individual protocols. All completed test material will be stored in a locked file cabinet in [name] laboratory at the VA Medical Center. A Privacy and Security Data Plan has been constructed to ensure confidentiality of all Sensitive Information (SI) and is outlined as follows:

MRI Risk Management Procedures:

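### In Phase I the parity of the subject ID gives the arm, which undermines the blinded retest promised for the imaging cohort

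*Combined protocol and SAP*

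**What the plan says.** **Allocation.** Section 9, Phase I, Procedures assigns participants by "alternating the assignments serially per each qualifying subjects' ID number that is assigned upon study entry". It spells the rule out: "subjects #'s 1100, 1102, 1104, etc will be assigned to the treatment group", while "subjects 1101, 1103, 1105, etc will be assigned to the waitlist group".

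**Staff.** The same paragraph has research assistants give the neuropsychological tests and a research assistant carry out the allocation. It blinds the group leader, but to test results and not to arm.

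**Labels.** Section 15, Phase I, protects confidentiality "by using coded numbers instead of names to identify individual protocols". Section 14, Phase I, MRI neuroimaging says of the scanning center: "Patients are only identified by their subject ID number assigned prior to scanning". That paragraph ends by giving the subject a further code for the images themselves.

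**Blinding.** The Phase I imaging paragraph of Section 9 opens with "we will recruit 60 additional individuals to complete the protocol as described above" and later states: "Participants will be retested by a group assignment-blinded examiner on the clinical and cognitive battery and imaging protocol". Within Phase I, examiner blinding to group is stated only there.

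**The concern.** A blinded examiner must not be able to work out the arm from the materials handled at testing. Here the identifier is itself the allocation code. If it is on the record form, blinding depends entirely on the examiner neither knowing nor noticing a rule that is printed in the protocol and applied by a colleague in the same staff category.

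The comparator is a wait-list, so participants know their arm. That leaves examiner blinding as the main protection against biased ratings. The retest battery in Section 9, Phase I, Assessments includes measures open to rater judgement, notably the HAMD-17 and NPI, as well as responses that have to be scored. Leniency toward CogSMART in administration, rating or scoring would look like a treatment effect.

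This is separate from the predictability of alternation at enrolment. That concerns who enters each arm; this concerns who rates them afterwards. A random list would not by itself ensure arm-neutral forms or keep the link away from assessors.

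**Working it through.** No power, alpha or sample-size figure is involved. The check sets the passages side by side.

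1. **Does the ID determine the arm?** The plan lists six IDs. The three even ones (1100, 1102, 1104) are treatment and the three odd ones (1101, 1103, 1105) are wait-list. The last digit classifies 6 of 6 correctly. For anyone who knows the rule, the probability of naming the arm is 1.0; by guessing under 1:1 allocation it is 0.5.

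2. **Is the ID on the test form?** Section 15 says coded numbers replace names on individual protocols. It does not say outright that the code is the subject ID. Section 12.10c describes study data as linked to sensitive information by a subject number, and no Phase I text introduces a second code for test forms. The subject ID is the natural reading, but it is an inference.

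3. **Can the examiner know the rule?** Allocation and testing are both given to research assistants. Nothing says they are different people, and nothing withholds the rule from examiners. Equally, nothing says that a retesting examiner did know it.

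4. **Where is blinding promised?** Only for the imaging cohort. For the 20 participants of Aims 1 and 2 there is no such statement.

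5. **Does the parity rule cover the imaging cohort?** That cohort follows the protocol already described and has no allocation mechanism of its own. Sixty consecutive IDs would split 60/2 = 30 per arm, matching the stated n = 30 each. This shows compatibility only, since any equal split gives 30 and 30. The paragraph also calls the assignment random and places it after baseline evaluation, whereas the parity rule uses an ID issued at entry. Parity is the natural reading, but not an explicit one.

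6. **Are image files labelled by parity?** Not on the text. The subject ID identifies the person at the center, and the images then get a further code.

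| Link in the chain | Status |
|---|---|
| ID parity gives the arm | Explicit |
| Form code is the subject ID | Close inference |
| Examiner knows or notices the rule | Possible, not stated |
| Imaging cohort allocated by parity | Natural reading, not explicit |
| Blinded retest promised | Explicit, imaging cohort only |
| Image files carry parity | Not shown |

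**The case against.** The strongest reply is that the allocation rule and the blinding statement stand in different paragraphs for nominally different cohorts, and that a label which can be decoded is not the same as an examiner who has decoded it. Both points stand. They limit the finding to a promise that the plan does not protect; they do not show that blinding failed.

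A reader might infer that blinding is lost for every Phase I participant. The documents do not support this: it would require every examiner to know the rule, and for the main 20 participants there is no blinding claim to lose. A reader might also infer that image analysts can read the arm from the scan label. The further image code in Section 14 tells against that.

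It can also be said that much of the retest battery is self-report (GDS, STAI, PDQ-39) or standardized (Digit Span, Digit Symbol Coding, Matrix Reasoning), and that wait-list participants may reveal their arm in any case. The first narrows the outcomes most exposed. The second is a reason not to add another, avoidable route.

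Finally, Section 9, Phase II, Participants speaks of Phase I attrition in the past tense, so at least part of Phase I has probably been run. That limits what can still be prevented and makes much of this a matter of reporting.

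**Conclusion.** The concern holds in a limited form. In Phase I an examiner or scorer who knows or notices the parity rule can read the arm from an ID-labelled form. This undermines the blinded retest stated for the imaging cohort, given as 60 participants in Section 9 (Section 10 allows up to 100). For the main 20-participant comparison it is an avoidable source of detection bias, not a contradiction.

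The conclusion rests on two close inferences: that the coded number on forms is the subject ID, and that the imaging cohort was allocated by the same rule. The decoding probability is 1.0 for someone with the rule. The resulting bias in any outcome cannot be derived from the documents, and I put no figure on it.

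A reader might extend this to the trial's primary result. The primary outcome is named under Phase II (Section 6, Hypothesis 1), and Phase II allocates in alternating runs of five, not by ID parity. A similar blinded-examiner sentence recurs in the Phase II imaging paragraph, but this rule does not bear on it. Severity is minor to moderate.

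**What to change.** - **Remaining Phase I assessments:** label test forms and scoring records with codes unrelated to arm. Have existing staff who do not test or score those participants hold the ID-to-arm link. State this in Section 9, Phase I, together with the allocation mechanism for the imaging cohort.
- **Data already collected:** Section 9, Phase I already requires double scoring. Do one pass under scrambled codes wherever recorded responses can be rescored. This cannot repair bias in how tests were administered, nor in HAMD-17 and NPI ratings made at interview.
- **Reporting:** do not describe assessments made under parity IDs as blinded unless it is documented that the examiners did not know the rule.

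The cost is minor relabelling work, a short protocol edit, some rescoring if the earlier double scoring is complete, and possible loss of the blinded description for Phase I data. No added visits are needed.
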